### Testing strategy

The primary endpoint will be confirmatorily tested in the pooled, overall population as well as in the two complementary subgroups of patients with PsA or axSpA.

If the null hypotheses has been rejected for the overall population, it will then be tested for both subgroups simultaneously, both at the significance level 0.05. If the null-hypothesis is false for the overall population, it can logically not be true for both complementary subgroups.

Therefore both subgroups can be tested at the same significance level  $\alpha = 0.05$  without any further adjustments for multiplicity of subgroups. This procedure provides strong control of the familywise type-I-error at  $\alpha = 0.05$ .

### 2.5.3 Handling of missing values/censoring/discontinuations

This study aims to estimate the magnitude of treatment effects that are obtainable under the respective treatments. The disease activity is expected to decrease in the course of treatment. If a patient drops out or discontinues the trial prematurely, the last observed value of that patient seems to be a proper estimate for the effect achieved in that patient.

For the primary endpoint, a patient with a missing assessment will be considered as a responder if he/she has met the response criterion already at the time of drop-out. Otherwise he/she will be considered as a non-responder.

## **2.6 Analysis of the key secondary objective**

Not applicable

## **2.7 Analysis of secondary efficacy objective(s)**

Secondary objectives

Refer to Table 1-1 of Section 1 for the list of secondary objectives.

### **2.7.1 Secondary endpoints**

Secondary efficacy evaluation will be performed on FAS.

Refer to Table 1-1 of Section 1 for the list of secondary endpoints.

### **2.7.2 Statistical hypothesis, model, and method of analysis**

The following hypotheses will be tested for the secondary objectives. All secondary endpoints will be tested exploratively outside the confirmatory framework:

H2: Secukinumab is not different to placebo regimen with respect to 10-point numerical rating scale (NRS) at Week 24.

H3: Secukinumab is not different to placebo regimen with respect to the respective subcomponent of the Psoriatic Arthritis Magnetic Resonance Imaging Score (PsAMRIS) in the affected foot at baseline at Week 24.

H4: Secukinumab is not different to placebo regimen with respect to resolution of enthesitis as assessed by the LEI at Week 24.

H5: Secukinumab is not different to placebo regimen with respect to physician's global assessment of disease activity at Week 24.

H6: Secukinumab is not different to placebo regimen with respect to patient's global assessment of disease activity at Week 24.

H7: Secukinumab is not different to placebo regimen with respect to physician's global assessment of heel enthesiopathy activity at Week 24.

H8: Secukinumab is not different to placebo regimen with respect to patient's global assessment of heel enthesiopathy acitivity at Week 24.

H9: The improvement in Secukinumab is not different to placebo regimen with respect to from Baseline in Short Form-36 Physical Component Summary (SF-36 PCS) or SF-36v2 at Week 24.

## **Analysis of secondary efficacy variables**

- Heel pain**

The mean change from Baseline of heel pain at 24 weeks, measured on a 10-point NRS will be analyzed using an Analysis of covariance (ANCOVA) model with factors treatment, country and diagnosis (PsA or axSpA) and with covariate baseline measurement of heel pain. The adjusted (LS) mean difference will be calculated as a point estimate together with its corresponding 95% confidence interval and p-value.

- Bone marrow oedema (PsAMRIS)**

The percentage of patients with an improvement of bone marrow oedema will be analyzed using a logistic regression model with factors treatment, country and diagnosis (PsA or axSpA). The odds ratio and its 95% confidence interval (CI) and p-value will be presented comparing secukinumab to placebo at Week 24.

- Enthesitis Assessment (LEI)**

The 4-site LEI (i.e. score with the four correct sites: lateral epicondyle humerus L + R and proximal achilles L + R) will be analyzed using a logistic regression model with factors treatment, country and diagnosis (PsA or axSpA). The odds ratio and its 95% confidence interval (CI) and p-value will be presented comparing secukinumab to placebo at Week 24.

- Physician's global assessment of disease activity**

Physician's assessment, measured on a VAS scale will be analyzed using an ANCOVA model with factors treatment, country and diagnosis (PsA or axSpA) and with covariate baseline value of global assessment of disease activity. The adjusted (LS-) mean difference will be calculated as a point estimate together with its corresponding 95% confidence interval and p-value.

- Physician's global assessment of heel enthesiopathy activity**

Physician's assessment, measured on a VAS scale will be analyzed using an ANCOVA model with factors treatment, country and diagnosis (PsA or axSpA) and with covariate baseline measurement of the global assessment of heel enthesiopathy. The adjusted (LS-) mean difference will be calculated as a point estimate together with its corresponding 95% confidence interval and p-value.

- Patient's global assessment of disease and heel enthesiopathy activity**

Refer to section 2.11 for analyses details.

- SF-36 or SF-36v2**

Refer to section 2.11 for analyses details

The time courses of secondary endpoints (percentage of patients with resolution of enthesitis as assessed by LEI, mean change from baseline for heel pain in NRS, Physician's / patient's

global assessment in VAS, etc.) will be summarized descriptively for all visits by treatment group, subgroup (PsA, axSpA) and overall from Baseline until Week 52.

Summary statistics will include relative and absolute frequencies for the binary variable 'resolution of enthesitis', and the number of patients (N), minimum, mean, median and maximum for the NRS/VAS variables. Additionally, these time courses will be displayed graphically.

### **Switching from placebo to secukinumab at Week 24**

At Week 24, patients originally randomized to placebo will switch to receive secukinumab 150 mg (1 injection of secukinumab 1 mL/150 mg) or secukinumab 300 mg (2 injections of secukinumab 1 mL/150 mg) in open-label fashion without a loading regimen.

Summary statistics will be provided for:

- Number and percentage of patients with resolution of Achilles tendon enthesitis after switching from placebo to secukinumab at Week 24.
- Mean change of heel pain in patients after switching from placebo to secukinumab at Week 24.

#### **2.7.3 Handling of missing values/censoring/discontinuations**

This study aims to estimate the magnitude of treatment effects that are obtainable under the respective treatments. The disease activity is expected to decrease in the course of treatment. If a patient drops out or discontinues the trial prematurely, the last observed value of that patient seems to be a proper estimate for the effect achieved in that patient.

For the confirmatory analyses of secondary endpoints related to physician's/patient's global assessment and SF-36, missing values will be replaced by the last observed value in that patient (Last Observation Carry Forward). In case of a substantial number of missing values, alternative approaches (RMREM, MI) may be additionally calculated as sensitivity analyses.

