Week	≤ -10	BSL	1	2	3	4	8	12	16	20	24 * TD/PPD	28	32	36	40	44	48	52 [*] TD/PPD	Unscheduled visit ^a	
Day	≤ -70	1	8	15	22	29	57	85	113	141	169	197	225	253	281	309	337	365		
Recommended visit window (± days)		± 2	± 2	± 2	± 2	± 2	± 5	± 5	± 5	± 5	± 2	± 2	± 2	± 5	± 2	± 2	± 2	± 2		
history																				
Demography	Х																			
PsA/axSpA medical history and previous therapies	х																			
Physical exam	S	S					S		S		S			S				S	S	
Height	Х																			
Weight	Х																			
Vital signs ^d	Х	Х		S		S	Х	S	Х	S	Х			Х				Х	Х	
QuantiFERON TB-Gold test	х																		Х	
Chest X-ray/MRI ^e	S																			
Serum pregnancy test	Х																		Х	
Urine pregnancy test		Х				Х	Х	Х	Х	Х	Х	Xf	Xf	Х	Xf	Xf	Xf	Х	Х	
Rheumatoid factor	Х																			
Anti-CCP	Х																			
Electrocardiogram ⁹		Х																Х	Х	

	Di Treatment Period 1												Treatment Period 2							
Visit	1	2	3	4	5	6	7	8	9	10	11	12	13	14	15	16	17	18	che	
Week	≤ -10	BSL	1	2	3	4	8	12	16	20	24 * TD/PPD	28	32	36	40	44	48	52 * TD/PPD	Unscheduled visit ^a	
Day	≤ -70	1	8	15	22	29	57	85	113	141	169	197	225	253	281	309	337	365		
Recommended visit window (± days)		± 2	± 2	± 2	± 2	± 2	± 5	± 5	± 5	± 5	± 2	± 2	± 2	± 5	± 2	± 2	± 2	± 2		
Randomization via IRT		Х																		
IRT contact such as for registration or drug supply including home administration	X	Х	Х	X	X	Х	X	Х	X	Х	Х	X	X	Х	X	X	X	Х		
Assessments only in Ps	A patier	nts																		
CASPAR criteria	Х																			
Assessments only in ax	SpA pat	ients																		
ASAS criteria/modified New York criteria ^h	Х																			

Page 49 Protocol No. CAIN457F3301

Confidential

Confidential

Page 50 Protocol No. CAIN457F3301

	Screening				٦	reatme	ent Per	iod 1						Trea	itment	Period	2		Unscheduled visit ^a
Visit	1	2	3	4	5	6	7	8	9	10	11	12	13	14	15	16	17	18	che
Week	≤ -10	BSL	1	2	3	4	8	12	16	20	24 * TD/PPD	28	32	36	40	44	48	52 * TD/PPD	Uns
Day	≤ -70	1	8	15	22	29	57	85	113	141	169	197	225	253	281	309	337	365	
Recommended visit window (± days)		± 2	± 2	± 2	± 2	± 2	± 5	± 5	± 5	± 5	± 2	± 2	± 2	± 5	± 2	± 2	± 2	± 2	
Assessments for all pation	ents																		
Heel pain		Х	Х	Х	Х	Х	Х	Х	Х	Х	Х			Х				Х	Х
MRI of the affected foot	Х										Х							Х	Х
Prior/Concomitant medication/non-drug therapy	Х	Х	Х	х	X	х	x	х	х	х	X	Xi	Xi	х	Xi	Xi	Xi	Х	х
AEs/SAEs ^j (including injection site reactions)	Х	Х	Х	х	X	х	х	х	х	х	X	Xĸ	Xĸ	х	Xk	Xĸ	X ^k	Х	х
LEI	Х	Х	Х	Х	Х	Х	Х	Х	Х	Х	Х			Х				Х	Х

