9.4.3 Handling of missing values/censoring/discontinuations

This study aims to estimate the magnitude of treatment effects that are obtainable under the respective treatments. The disease activity is expected to decrease in the course of treatment. If a patient drops out or discontinues the trial prematurely, the last observed value of that patient seems to be a proper estimate for the effect achieved in that patient.

For the primary endpoint, a patient with a missing assessment will be considered as a responder if he/she has met the response criterion already at the time of drop-out. Otherwise he/she will be considered as a non-responder.

For the confirmatory analyses of secondary endpoints related to physician's/patient's global assessment and SF-36, missing values will be replaced by the last observed value in that patient (Last Observation Carry Forward). In case of a substantial number of missing values, alternative approaches (RMREM, MI) may be additionally calculated as sensitivity analyses.

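### LOCF with a Week 24 ANCOVA is the main analysis for five exploratory secondary endpoints, and heel pain has no missing-data rule; a repeated-measures model on the nine scheduled visits would be a cheap improvement

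*SAP*

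**What the plan says.** **Missing data.** SAP 2.7.3 and protocol 9.4.3 share one rule: "missing values will be replaced by the last observed value in that patient (Last Observation Carry Forward"). It covers five endpoints: physician's and patient's global assessment of disease activity, the same two for heel enthesiopathy activity, and SF-36. The reason given is that disease activity should fall during treatment and that, for a patient who drops out, "the last observed value of that patient seems to be a proper estimate for the effect achieved in that patient". If a substantial number of values is missing (no threshold is set), "alternative approaches (RMREM, MI) may be additionally calculated as sensitivity analyses".

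**Model.** Each endpoint has a single-visit ANCOVA at Week 24 (SAP 2.7.2, 2.11 and the code in 5.4.3). For heel pain it is fitted "with factors treatment, country and diagnosis (PsA or axSpA) and with covariate baseline measurement of heel pain". Heel pain is not among the endpoints that the LOCF sentence names, and no other rule is given for it.

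**Data.** Protocol Table 6-1 schedules all six scales at Baseline and Weeks 1, 2, 3, 4, 8, 12, 16, 20 and 24. Patients who stop during Treatment Period 1 have the Week 24 assessments four weeks after their last dose (protocol 5.6.2).

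**Status.** SAP 2.7.2 says: "All secondary endpoints will be tested exploratively outside the confirmatory framework". SAP 2.7.3 nevertheless calls the analyses of these same endpoints confirmatory.

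**The concern.** The rationale works against the method. If disease activity keeps falling, a value carried from an early visit is not the Week 24 value, and the objectives are stated at Week 24. What matters for the comparison is whether the two arms lose the same amount of later improvement.

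Unequal, outcome-related drop-out is plausible here. Patients stay on placebo for 24 weeks, those rescued with prohibited treatments before the Week 24 assessments are discontinued, and patients not benefiting may leave (protocol 5.5.6). If more placebo patients leave early with poor scores, LOCF freezes them there and flatters secukinumab. If more secukinumab patients leave early, the effect shrinks.

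The early-termination visit adds an ambiguity. A patient whose last dose was at Week 8 is assessed at about Week 8 + 4 = Week 12, on a visit labelled Week 24. The available text does not say whether that value enters as Week 24 data, so it could also supply the Week 24 heel pain score.

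At stake are the estimates, intervals and p-values for six reported secondary endpoints.

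**Working it through.** **1. What the plan gives.** It has no figure for this analysis. The nearest is the sample-size allowance (protocol 9.8, SAP 3): 89 evaluable and 100 randomised per arm, so 1 - 89/100 = 11%, and 89/(1 - 0.11) = 100. This also covers other protocol violations, so it is only a rough guide to drop-out.

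**2. Assumptions (not from the documents).** SD 25 mm on a 100 mm VAS; placebo change -15 mm; true Week 24 difference 0 or -10 mm with gradual onset; correlation between visits 0.5 + 0.5 × exp(-lag/12 weeks). Drop-out is monotone and missing at random, either unrelated to the score or linked to the last observed score. There are 100 patients per arm and nine post-baseline visits, with country and diagnosis omitted, and 1,500 simulated trials per setting. LOCF-ANCOVA is compared with an unstructured repeated-measures likelihood model (MMRM).

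**3. Results.** Negative bias favours secukinumab.

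| True effect (mm) | Drop-out placebo / active | Linked to score | LOCF bias | LOCF SE | LOCF coverage | MMRM bias | MMRM SE | MMRM coverage |
|---|---|---|---|---|---|---|---|---|
| 0 | 10.6% / 10.7% | no | 0.09 | 2.88 | 94.7% | 0.10 | 3.11 | 94.9% |
| 0 | 21.6% / 21.6% | no | -0.08 | 2.83 | 94.5% | -0.08 | 3.28 | 94.9% |
| 0 | 14.9% / 5.5% | no | -0.64 | 2.88 | 94.8% | 0.05 | 3.11 | 95.7% |
| 0 | 17.8% / 6.7% | yes | -1.60 | 2.93 | 90.9% | -0.16 | 3.13 | 95.8% |
| 0 | 34.5% / 11.3% | yes | -2.96 | 2.91 | 83.1% | 0.05 | 3.34 | 95.5% |
| 10 | 10.6% / 10.6% | no | 0.48 | 2.90 | 95.2% | -0.04 | 3.11 | 95.3% |
| 10 | 21.7% / 21.5% | no | 0.90 | 2.88 | 94.9% | -0.18 | 3.28 | 96.0% |
| 10 | 9.1% / 30.9% | no | 3.31 | 2.90 | 78.5% | 0.01 | 3.28 | 94.9% |
| 10 | 12.1% / 32.8% | yes | 4.47 | 3.00 | 67.7% | -0.08 | 3.33 | 94.1% |

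The simulation error of a bias is about 2.9/√1500 = 0.07 mm, so the first two biases cannot be told from zero.

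**4. Plausibility of the bias.** LOCF bias is roughly the drop-out share times the improvement missed, differenced between arms. In the third row, 0.64/(0.149 - 0.055) = 6.8 mm missed per extra placebo drop-out, which is credible against an assumed total change of 15 mm.

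**5. Where coverage is lost.** If the standard error is right and only bias b matters, coverage is Φ(1.96 - |b|/SE) - Φ(-1.96 - |b|/SE).
- 17.8% / 6.7%: 1.60/2.93 = 0.546, so Φ(1.414) - Φ(-2.506) = 0.921 - 0.006 = 91.5% (simulated 90.9%).
- 34.5% / 11.3%: 2.96/2.91 = 1.017, so Φ(0.943) - Φ(-2.977) = 0.827 - 0.001 = 82.6% (simulated 83.1%).

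Bias alone accounts for the loss. LOCF standard errors also stayed within about 6% of the estimator's own sampling SD.

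**6. Interval width against MMRM.** At 11% drop-out, 1 - 2.88/3.11 = 7% narrower. At 22%, 1 - 2.88/3.28 = 12% to 1 - 2.83/3.28 = 14% narrower.

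**The case against.** **Status.** These endpoints lie outside the confirmatory framework, SAP 3 asks for careful interpretation of secondary results, and the primary endpoint has its own missing-data rule. This stands and sets the weight of the point.

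**Size.** If drop-out is near the plan's 11% allowance and equal between arms, bias is 0.1 to 0.5 mm with 95% coverage. This also stands.

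**Intervals.** A reader might infer that LOCF makes the confidence intervals invalid whenever values are missing. The check does not support that: being narrower than another method's interval is not the same as undercovering, and coverage stays near 95% with equal drop-out.

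**Heel pain.** A reader might infer that heel pain falls under LOCF, or that it defaults to complete cases. The documents establish neither. The general last-value rationale could be stretched to it, but the operative sentence leaves it out. The rule is simply unstated.

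**Fairness of the test.** Drop-out was generated as missing at random, which favours MMRM, and no missing-not-at-random case was run. This limits the claim. It does not rescue LOCF, which was biased under unequal drop-out even when drop-out was unrelated to the score.

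**Different question.** LOCF can be defended as describing the effect reached when a patient leaves. The stated endpoints, however, are changes at Week 24.

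**Conclusion.** The point holds as a cheap improvement. LOCF is an avoidable main analysis for five exploratory endpoints, and heel pain lacks a rule. The risk is bias under unequal drop-out, in either direction. With no true effect and score-linked drop-out it is 1.6 mm at 18%/7% (1.6/25 = 0.06 SD) and 3.0 mm at 35%/11% (3.0/25 = 0.12 SD). Two-sided false-positive rates are then 100 - 90.9 = 9% and 100 - 83.1 = 17% instead of 5%. With a true 10 mm effect, 9%/31% drop-out attenuates it by 3.3 mm. MMRM bias was at most about 0.2 mm throughout.

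All of this rests on an assumed SD, effect, onset, correlation and drop-out pattern; SF-36 was not simulated on its own scale. A reader might go further and infer that LOCF systematically favours secukinumab or endangers the trial's conclusion. The documents support neither: the direction depends on which arm loses more patients, and no confirmatory decision uses these endpoints.

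**What to change.** - **Main analysis.** Use an MMRM on observed data over the nine post-baseline visits for heel pain, the four global assessments and SF-36. Include treatment, visit, treatment-by-visit, country, diagnosis, baseline and baseline-by-visit, with unstructured covariance and the Week 24 contrast. Country stays, as in the present models. Nine visits give 9 × 10/2 = 45 covariance parameters, so name a fallback structure in advance.
- **Early-termination visits.** Assign these assessments to the study week in which they took place.
- **Sensitivity.** Keep LOCF-ANCOVA. A missing-not-at-random analysis would be a sensible addition, since the MMRM assumes missing at random.
- **Text.** Update SAP 2.7.2, 2.7.3, 2.11 and the code in 5.4.3. Remove the last-observed-value rationale from SAP 2.7.3 only, because the same sentence also supports the primary-endpoint rule in SAP 2.5.3 and protocol 9.4.3. In SAP 2.7.3, replace confirmatory with exploratory, to match 2.7.2.
- **Record.** Protocol 9.4.3 also prescribes LOCF, so enter the change in SAP Section 4 (now marked not applicable) or amend the protocol, before the Week 24 unblinding.

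**Cost.** No new data; text and standard code. Intervals widen somewhat: in the simulation by 3.11/2.88 - 1 = 8% at 11% drop-out, and by 14% (3.28/2.88 - 1) to 16% (3.28/2.83 - 1) at 22%.

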### **2.8 Safety analyses**

For all safety analyses, the Safety set will be used.

Summaries will be performed separately for first (Week 1-24) and entire treatment periods. Use of data up to and including the last visit before rescue provides and unbiased comparison between secukinumab and placebo; data collected beyond week 24 are included in analyses which summarize the entire treatment period.

Safety analyses will be performed by PsA and AxSpA patients on treatment received or actual treatment as described below:

The actual treatment or treatment received for summaries of safety data will differ to the treatment assigned at randomization only if a subject received the wrong treatment during the entire study.

For those patients who received not the treatment randomized, i.e. who received erroneously the wrong treatment at least once, an additional AE listing will be prepared displaying which events occurred after the treatment errors.

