**On-treatment period:** The period where the patients are exposed to the study treatment. For this study the treatment phase consists of 52 weeks (for treatment group 1) for secukinumab, and 24 weeks of on-treatment period for placebo and 28 weeks of on treatment for secukinumab (for treatment group 2).

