#### **Duration of exposure**

The duration of exposure to study treatment will be summarized by treatment group.

In addition, the number and percentage of patients with cumulative exposure levels (e.g. any exposure,  $\geq 1$  week,  $\geq 2$  weeks,  $\geq 3$  weeks,  $\geq 4$  weeks,  $\geq 8$  weeks, etc.) will be presented.

Duration of exposure will be defined as the time from first dose of study treatment to the time of treatment switch (for patients who switch treatment) or end of treatment period (whichever is first). For patients who discontinue, this will be the subject's last visit in the corresponding treatment period.

Duration of exposure (years) = duration of exposure (days) / 365.25

Duration of exposure (100 subject years) = duration of exposure (years) / 100

The analyses of duration of exposure described above will be done for both the study treatment periods.

**Compliance** will be calculated based on documented study drug administrations and syringe counts and displayed by treatment group.

Compliance is expected to be 100%, unless temporary interruption is needed for safety reasons. Compliance will also be assessed by a Novartis monitor using information provided by the authorized site personnel.

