### **2.8.1 Adverse events (AEs)**

The crude incidence of treatment emergent adverse events (i.e. events started after the first dose of study treatment or events present prior to the first dose of study treatment but increased in severity based on preferred term) will be summarized by primary system organ class and preferred term. Confidence intervals for the crude rate will be derived as described in Section

In addition, exposure time-adjusted rates (incidence rate) including 95% confidence intervals will be provided for the entire treatment period to adjust for differences in exposure between treatment groups. Graphical displays of the crude incidence and exposure-adjusted rates will be presented for all AEs and serious AEs by system organ class.

Treatment emergent adverse events reported will be presented by preferred term in descending frequency according to its incidence in total secukinumab group (combining all secukinumab treatment groups) starting from the most common event. Summaries (crude incidences only) will also be presented for AEs by severity and for study treatment related AEs. If a particular AE 'severity' is missing, this variable will be listed as missing and treated as missing in summaries. If a subject reported more than one adverse event with the same preferred term, the adverse event with the greatest severity will be presented. If a subject reported more than one adverse event within the same primary system organ class, the subject will be counted only once with the worst severity at the system organ class level, where applicable.

Separate summaries will be provided for

- adverse events suspected to be related to study drug by the investigator
- deaths
- serious adverse events
- adverse events leading to discontinuation
- adverse events leading to temporary dose interruption

Adverse events will also be reported separately by MedDRA SMQ.

For all adverse event summaries, the MedDRA version used for reporting the study will be described in a footnote.

Adverse event summaries will also be provided for the follow-up period for all patients (completers and early discontinuations).

A listing of non-treatment emergent adverse events will be provided. These cover adverse events that occurred before the first dose of the study treatment. The crude incidence will be provided without treatment information.

Algorithms for date imputations will be provided in Programming Specifications.

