**Table 2.8-1 Overview of analyses on some safety endpoints**

Analysis period	AEs & SAEs	AEs by severity	Study drug related AEs	AEs-SMQ	Risk	Notables for (vitals/ECG), lab criteria
Day 1 – Week 24	• crude incidence	• crude incidence	• crude incidence	• crude incidence	• crude incidence	• crude incidence
Day 1 – Week 24	• exposure time adjusted incidence*					
Entire Treatment (up to week 52)	• crude incidence • exposure time adjusted incidence*	• crude incidence	• crude incidence	• exposure timeadjusted incidence	• crude incidence exposure time adjusted incidence	• crude incidence

\*Exposure-adjusted incidence rates will be done for the following:

- at the PSOC for AE and SAE
- at the PT level for common AEs, which is defined as at least 2% of the patients in the combined AIN457 groups during the initial treatment period or events that had an incidence rate of at least 5.0 cases per 100 subject-years in the combined AIN457 groups during the entire treatment period
- at Level 1 for Risks and SMQ analyses

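### Read literally, SAP 2.8 leaves secukinumab events after the Week 24 switch under Group 2's randomized treatment in the 52-week safety tables, and the SAP does not say which exposure the 52-week rates use

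*SAP*

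**What the plan says.** **Treatment label.** SAP 2.2 analyses the safety set by treatment received. SAP 2.8 then explains that term: actual treatment "will differ to the treatment assigned at randomization only if a subject received the wrong treatment during the entire study". The next paragraph asks for an extra listing for patients who were given the wrong treatment at least once. Neither paragraph mentions the planned switch.

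**Data included.** SAP 2.8 plans summaries for Weeks 1 to 24 and for the entire treatment period, and "data collected beyond week 24 are included in analyses which summarize the entire treatment period".

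**The switch.** Protocol 3.1 and 5.2 and SAP 1.1 move every placebo patient to secukinumab at Week 24. SAP 2.1.1 gives "24 weeks of on-treatment period for placebo and 28 weeks of on treatment for secukinumab (for treatment group 2").

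**Exposure.** SAP 2.4.1 defines duration of exposure as the "time from first dose of study treatment to the time of treatment switch (for patients who switch treatment") or to the end of the treatment period, whichever comes first, and converts it to units of 100 subject-years. It adds: "The analyses of duration of exposure described above will be done for both the study treatment periods".

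**Rates.** SAP 2.8.1 says that "exposure time-adjusted rates (incidence rate) including 95% confidence intervals will be provided for the entire treatment period", in order to adjust for exposure differences between groups. It orders events "according to its incidence in total secukinumab group (combining all secukinumab treatment groups"). Table 2.8-1 gives exposure-adjusted rates at preferred-term level to events seen in "at least 2% of the patients in the combined AIN457 groups during the initial treatment period or events" with at least 5.0 cases per 100 subject-years in those groups over the entire period. The SAP does not say who belongs to the pooled groups.

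**The concern.** A planned switch is not wrong treatment, so the one labelling rule in SAP 2.8 leaves Group 2 under its randomized treatment to Week 52. SAP 1.1 names that group placebo. A programmer following the text could therefore count 28 weeks of secukinumab events in a placebo column.

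The exposure text adds a second problem. Duration of exposure in SAP 2.4.1 stops at the switch, while the events in the entire-period tables run to Week 52. The analysis is to be done for both periods, but no start point is given for exposure after the switch; the first dose of study treatment in Group 2 is a placebo dose. SAP 2.8.1 does not refer back to 2.4.1 and does not say how time after a first event is handled.

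Two competent programmers could thus produce different 52-week adverse event tables from the same SAP. Depending on the choice, a real excess on secukinumab could look smaller, or the direction of the comparison could reverse. Overall safety and tolerability is a stated secondary objective.

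**Working it through.** The plan states no figure for this point, so there is none to reproduce. The check is person-time arithmetic.

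**Inputs.** From the documents: about 200 patients randomized 1:1, so about 100 per arm; switch at Week 24; follow-up to Week 52; 365.25 days per year (SAP 2.4.1). Assumed: constant event rates, no dropout, placebo rates of 5 per 100 subject-years (the threshold in Table 2.8-1) and 20 per 100 subject-years. R is the true secukinumab-to-placebo rate ratio.

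**Subject-years.**
- 24 weeks: 100 × 168 / 365.25 = 46.0
- 28 weeks: 100 × 196 / 365.25 = 53.7
- 52 weeks: 100 × 364 / 365.25 = 99.7
- Split at the switch: placebo 46.0; any secukinumab 99.7 + 53.7 = 153.3 (before rounding), of which 53.7 / 153.3 = 35% comes after the switch.

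**Reading A: Group 2 headed placebo, 52 weeks of events over 52 weeks of exposure.** For all events the observed ratio is R / [(24 + 28R) / 52].
- R = 1.5: 1.5 / (66/52) = 1.18
- R = 2: 2 / (80/52) = 1.30
- R = 3: 3 / (108/52) = 1.44

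**Reading B: 52 weeks of events over exposure that stops at the switch.** The observed ratio is R / [(24 + 28R) / 24].
- R = 1: 24/52 = 0.46, so the placebo rate is inflated 52/24 = 2.17-fold.
- R = 2: 2 / (80/24) = 0.60, so the direction reverses.
- For first events at equal rates, with t = 24/52 year and 52 weeks taken as one year, the inflation is [1 − exp(−L)] / [1 − exp(−Lt)]: 4.88% / 2.28% = 2.14 at L = 0.05, and 18.13% / 8.82% = 2.06 at L = 0.20.

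**Reading C: events and person-time both split at the switch.** Under constant rates the observed rate ratio equals R.

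**Crude incidence under a 52-week placebo heading.** No exposure definition is needed. The ratio is [1 − exp(−L1)] / [1 − exp(−L0·t − L1(1 − t))], where L0 is the placebo rate and L1 the secukinumab rate.
- L0 = 0.05, L1 = 0.10: 9.52% / 7.40% = 1.29, against 1.98 at Week 24.
- L0 = 0.20, L1 = 0.40: 32.97% / 26.49% = 1.24, against 1.91 at Week 24.

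**Crude incidence by treatment at onset, equal true rates.** Splitting has its own distortion here, because follow-up is 24 weeks on placebo but 52 or 28 weeks on secukinumab.
- 5 per 100 subject-years: placebo 2.28%; any secukinumab (4.88% + 2.66%) / 2 = 3.77%; ratio 1.65.
- 20 per 100 subject-years: placebo 8.82%; any secukinumab (18.13% + 10.21%) / 2 = 14.17%; ratio 1.61.

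**Selection of preferred terms.** 20,000 trials were simulated with 100 patients per arm. The pooled group for the 52-week criterion was taken either as Group 1 alone or as Group 1 plus Group 2 after the switch. The two definitions selected differently in at most about 6% of trials at constant rates of 1 to 8 per 100 subject-years. They differed in about 35% for a contrived event with no risk in the first 24 weeks on drug and 10 per 100 subject-years afterwards.

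**The case against.** The best defence is that the sentence in SAP 2.8 is about dosing errors. It speaks of wrong treatment, and so does the paragraph after it. Protocol 5.2 describes Group 2 as placebo followed by secukinumab, so keeping patients in their randomized group can mean keeping them in a sequence, which agrees with SAP 2.1.1. No text heads a 52-week column as placebo. The safety set is analysed by treatment received, exposure is cut at the switch, and the pooled secukinumab wording hints at a split. Protocol 9.5.2.1 also allows adverse events to be shown separately before and after Week 24.

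Most of this stands as a reading of intent. A reader might infer that the SAP deliberately counts switched patients as placebo; the documents do not say so. A reader might also infer that the SAP has no denominator at all; that is wrong, because SAP 2.4.1 defines exposure in subject-years and Table 2.8-1 uses the same unit. Nor does the SAP instruct anyone to divide 52-week events by 24-week exposure; that is one way of combining 2.8 with 2.4.1. The section number missing after the confidence-interval sentence in 2.8.1 may be an extraction loss and is not counted here.

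The defence does not close the gap. If the sentence covers dosing errors only, the SAP has no stated rule for switched patients. The presentation by period in Protocol 9.5.2.1 is optional, and SAP 2.8 plans entire-period tables. No visible text matches 52-week events to a stated person-time.

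**Conclusion.** The point holds as a defect in SAP wording that can produce wrong 52-week safety tables. Applied literally, the rule in 2.8 puts post-switch secukinumab events under Group 2's randomized treatment, and the exposure for the rates is not tied down. The size depends on the reading. A true rate ratio of 2 shows as about 1.3 if 52 weeks of events and exposure carry a placebo heading. The placebo rate is inflated up to 2.17-fold at equal true rates if exposure stops at the switch. A split of both events and time gives no bias in the rates. These figures assume constant rates and no dropout, and the event rates are illustrative.

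It would be too strong to infer that the trial's safety comparison is compromised. The controlled Day 1 to Week 24 tables and the deaths by period (SAP 2.8.2) are unaffected, efficacy is untouched, and the affected tables are descriptive. The effect on which preferred terms receive exposure-adjusted rates is minor except for late-emerging events. The text should be corrected before the entire-period tables are programmed.

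**What to change.** 1. In SAP 2.8, state that the sentence on actual treatment applies to dosing errors only, not to the planned Week 24 switch.
2. For entire-period exposure-adjusted rates, assign both events and person-time by treatment at onset. Placebo runs from Day 1 to the first secukinumab dose. Any secukinumab is Group 1 from Day 1 plus Group 2 from its first secukinumab dose.
3. Cite that person-time as the denominator in 2.8.1 and Table 2.8-1, and say whether time is censored at the first event.
4. Define the total secukinumab group and the combined AIN457 groups as any secukinumab.
5. For entire-period tables that give crude incidence only (by severity, drug-related), show Group 2 as one column labelled 'placebo then secukinumab'. Otherwise state that follow-up differs and do not compare crude percentages between placebo and any secukinumab, because unequal follow-up alone gives a crude ratio of about 1.6. The same caution applies wherever entire-period crude incidence is shown beside a rate.

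The cost is SAP wording, table shells, a little extra programming and the caveat on the crude tables. Dose dates are already recorded (Protocol 6.3), so no new data are needed.
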